Statistical analysis

Project title: Micronutrient Supplementation for Women With PCO-syndrome - Influence of Nutrition and Physiology on the Development of PCOS-typical Parameters

NCT number: N/A

Participants

Investigator:

Assoc.[name].Doiz. [name]

Participating doctors

Assoc.[name].Doiz. [name]

Participating clinics

Medical University of Vienna
Department of Obstetrics and Gynecology
Clinical Division of Gynecologic Endocrinology and
Reproductive Medicine
[name]
[name]
Tel: [name]
Fax: [name]

Sample size calculation:

Assuming a reduction of the mean AMH levels by 2 ng/ml at a standard deviation of 3 ng/ml and an alpha value of 0.05 and a power of 0.90, the paired t-test requires 26 patients per group. Due to the fact that the participants wish to conceive a child and have been diagnosed with sterility, a low drop-out rate can be expected. There is no reliable data on this or similar treatments that allow prediction of the chance to conceive. Due to the favourable benefit-to-risk profile, a 15% drop-out rate is assumed. This corresponds to 4 patients per group. Thus, the final sample size is calculated as 30 patients per group, which leads to a total study population of 60.

Parameters obtained during routine clinical examinations:

All parameters on outcome (AMH = anti-müllerian hormone, total testosterone and androstendion levels) will be obtained during routine clinical examinations.

Several additional parameters will also be collected and included in the database. They do not require additional effort on behalf of the patients. They include: general patient information (age, duration of infertility, height and body weight, additional medication); information pertaining to PCO-syndrome (menstruation history, Ferriman-Gallwey-score on hirsutism (if applicable), acne, scalp-hair effluvium); hormone parameters on days 2 to 5 of the menstrual cycle (androstendion, thyroid-stimulating hormone, luteal hormone, follicle-stimulating hormone, sex hormone binding globulin); as well as an oral glucose tolerance test, which is routinely performed by general practitioners.

In addition, the individual development of the fertility treatment will be documented for a maximum of 6 months following active study participation.

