The bio-statistician will randomise the data using nQuery advisor™ Version 7.0. The information will then be packaged in an envelope by a person independent of the participating medical professionals and other scientific personnel. This will only be opened after the inclusion of the patient. Categorical variables will be presented as absolute numbers and percentages, numerical variables as median and interquartile range.

Final statistical analysis:

The following statistical analyses are planned: The result parameters and the patient characteristics of the two groups will be compared using the Welch test (for numerical variables) and the Chi-square-test or Fisher's exact test (for categorical variables). A p-value of <0.05 is considered to be statistically significant. The analysis will be performed as an intention-to-treat analysis. The statistical analyses will be performed using SPSS 24.0 for Windows (SPSS Inc., 1989-2017).

Overview on parameters to be analysed:

Parameter	Unit	Type	Planned statistical test
Age	Years	Numerical	Welch test
Body mass index	Kg/m ²	Numerical	Welch test
Sterility: Secondary (versus primary)	n (%)	Categorical	Chi-square/Fisher's exact test
Duration of infertility	Years	Numerical	Welch test
Pre-treatment FSH	mU/mL	Numerical	Welch test
Pre-treatment LH	mU/mL	Numerical	Welch test
Pre-treatment AMH	ng/mL	Numerical	Welch test
Pre-treatment testosterone	ng/mL	Numerical	Welch test
Pre-treatment androstenedione	ng/mL	Numerical	Welch test
Post-treatment AMH	ng/mL	Numerical	Welch test
Post-treatment testosterone	ng/mL	Numerical	Welch test
Post-treatment androstenedione	ng/mL	Numerical	Welch test

Abbreviations used: n (%) = number (frequency)

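### Does applying p<0.05 to AMH, testosterone and androstenedione alike inflate the trial's false-positive rate?

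*SAP*

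**What the plan says.** In the SAP's Sample size calculation, AMH is the only outcome with design assumptions: "Assuming a reduction of the mean AMH levels by 2 ng/ml at a standard deviation of 3 ng/ml", together with "an alpha value of 0.05 and a power of 0.90, the paired t-test requires 26 patients per group".

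The section on parameters obtained during routine examinations then names three outcomes in one list, AMH first: "All parameters on outcome (AMH = anti-müllerian hormone, total testosterone and androstendion levels) will be obtained during routine clinical examinations".

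Under Final statistical analysis, one sentence covers outcomes and patient characteristics together: "The result parameters and the patient characteristics of the two groups will be compared using the Welch test (for numerical variables", with the chi-square or Fisher test for categorical variables. The threshold follows: "A p-value of <0.05 is considered to be statistically significant".

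The closing overview table has twelve rows. Nine are pre-treatment characteristics and three are the post-treatment hormones, such as "Post-treatment testosterone". Each post-treatment row carries the Welch test. The SAP does not label any outcome primary or secondary, set a testing order, adjust for multiplicity, or say which result supports a conclusion of efficacy.

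**The concern.** The two parts of the SAP seem to pull in different directions. The sample size treats AMH as the outcome that matters, with alpha 0.05 spent on it. The analysis section puts the two androgens beside AMH, with the same test and the same threshold. Read literally, a trial with a non-significant AMH difference and a significant testosterone difference has produced a significant outcome result, and nothing in the SAP says what status that result has.

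The overall false-positive rate is at stake. Three chances at 5% give more than 5% unless the tests are perfectly correlated. All of the excess comes from trials in which an androgen is significant and AMH is not. A reader could fear that such a trial would be reported as positive.

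**Working it through.** **Inputs.** From the SAP: AMH reduction 2 ng/ml, SD 3 ng/ml, alpha 0.05, power 0.90, paired t-test, 26 per group, 15% drop-out, 30 per group (Sample size calculation); three outcomes; one threshold of 0.05 (Final statistical analysis). Assumed: the correlation between outcomes, taken from 0 to 0.9 because the SAP gives none.

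**The plan's own figure.** The standardised effect is 2/3 = 0.67. For a paired t-test, exact power from the noncentral t distribution first reaches 0.90 at n = 26 two-sided (power 0.904). One-sided, it would be 21. So the stated 26 reproduces, and it shows that the alpha is two-sided. Drop-out: 15% of 26 = 3.9, rounded to 4, and 26 + 4 = 30. The alpha here belongs to a single test, on AMH.

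**If AMH alone decides.** The error is 5% two-sided, or 2.5% counting only differences in the beneficial direction.

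**If any one of three sufficed**, with no true effect on any of them:

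- Uncorrelated, two-sided: 1 − 0.95³ = 1 − 0.8574 = 0.1426.
- Uncorrelated, beneficial direction only: 1 − 0.975³ = 1 − 0.9269 = 0.0731.
- Common correlation r, two-sided: 1 − ∫ φ(u) [Φ((1.96 − √r·u)/√(1−r)) − Φ((−1.96 − √r·u)/√(1−r))]³ du. For the beneficial direction, drop the second Φ term.
- Upper bound under any dependence: 3 × 0.05 = 0.15 two-sided; 3 × 0.025 = 0.075 beneficial direction.

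| Correlation (assumed) | Two-sided | Beneficial direction | Two-sided excess over 0.05 |
|---|---|---|---|
| 0 | 0.1426 | 0.0731 | 0.0926 |
| 0.5 | 0.1254 | 0.0627 | 0.0754 |
| 0.9 | 0.0836 | 0.0418 | 0.0336 |

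Simulated Welch tests at 30 per group agree: two-sided 0.142 at r = 0 and 0.085 at r = 0.9. If only the two androgens correlate (0.5 to 0.9) and AMH is independent of both, the two-sided figure is 13.6% to 11.7%.

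**Which branch does the SAP describe?** The arithmetic cannot settle this; the text has to.

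1. The threshold sentence follows one that covers outcomes and patient characteristics alike. It therefore applies equally to age, body mass index and pre-treatment FSH. Nobody would infer that a baseline age difference ranks with AMH as evidence of efficacy, so a shared threshold does not imply a shared rank.
2. No sentence says that a significant result on any one outcome establishes efficacy.
3. The only ranking signal in the document points to AMH: it alone has an assumed effect, SD, alpha and power, and it heads the list of outcomes.

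The text fits the 5% branch. The 8% to 14% range is the error rate of a rule that the SAP does not contain.

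**The case for a change.** The best argument for a change is that the SAP is where the significance rule is set, so it should carry the priority even if the protocol also does. As written, it neither permits nor excludes an efficacy claim resting on an androgen alone. One sentence fixed before the data are seen would close that route at no cost in patients and without touching the AMH test.

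The situation is also realistic. If 2 and 3 ng/ml are read as the between-group difference and SD (an assumption), a two-sample test at 30 per group has about 72% power. AMH could then miss significance despite a true effect, which would make an androgen-only claim tempting.

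Part of this stands. The SAP does lack a primary label, and a sentence naming one would make it clearer. But silence about a misuse is not permission for it, and the primary outcome is commonly named in the protocol, with which any added sentence would have to agree. The 72% figure arises because the sizing test differs from the analysis test. That is a separate question, and it does not change the multiplicity argument. The two-sided 8% to 14% also counts differences in the harmful direction. For false claims of benefit, the same hypothetical rule gives 4.2% to 7.3%, against 2.5% for AMH alone.

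**Conclusion.** The concern does not call for a change. The quoted text and the arithmetic are both right, but the inflated rates follow only if any one of three outcomes may establish efficacy, and the SAP does not say so. On the reading its sample size supports, AMH decides and the two-sided error is the planned 5%.

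What remains is a missing label that a competent analyst would supply from the sample size section or the protocol, treating the two androgens as supportive.

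This conclusion assumes that the protocol does not give the three outcomes equal standing as alternative routes to an efficacy claim. If it did, the 14.3% to 8.4% two-sided range (correlation 0 to 0.9, no true effects) would become relevant. Nothing in the SAP points that way.
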